13.4 Planned PK, PD, and immunological variable analysis

Certolizumab pegol plasma concentrations levels at Week 16 and Week 48 will be assessed as primary variables in this study. Other PK and immunological variables include CZP plasma concentrations at other study timepoints and anti-CZP antibody levels throughout the study.

Plasma CZP concentrations will be used to build a PopPK model with the nonlinear mixed-effect modeling (NONMEM) software. The model will be parameterized in terms of clearance, volume of distribution, and absorption rate constant. Details of the PopPK modeling procedures will be described in a separate data analysis plan. The pediatric PopPK model will be combined with PD data (PedACR) and if the data allow, an exposure response relationship will be derived. These modeling analyses and results will be reported separately.

All study participants enrolled following Protocol Amendment 9 will have plasma CZP concentrations and anti-CZP antibodies analyzed using the ECLIA method. In addition, PK and ADA samples (for which sufficient volume is available) collected in this study prior to Protocol Amendment 9 will be analyzed with the ECLIA method.

Data from the ECLIA method will constitute the study's main PK and anti-CZP antibody evaluations. As such, PK and anti-CZP antibody data generated with the original ELISA method will be reported as Listings. Plasma CZP concentration data generated by the ECLIA method will be tabulated and summarized (geometric mean, arithmetic mean, minimum, maximum, standard deviation and % coefficient of variation) by study dose regimen (original CZP dose regimen or reduced CZP dose regimen) for each PK sampling visit. Plasma concentration time curves will be plotted, along with respective individual anti-CZP antibody titers where available, separately for study participants who began treatment according to the original CZP dose regimen or the reduced CZP dose regimen, overall, and by Baseline age stratum. Subgroup analyses will include study participants enrolled with Protocol Amendment 9 and those treated up to the Week 16 timepoint under the original maintenance dosing regimen. Where available, individual ECLIA-based anti-CZP antibody data will be tabulated by study visit and Baseline age stratum (all study participants, 2 to 5 years, 6 to

11 years, and 12 to 17 years). In addition, safety and efficacy profiles by antibody titers (or titer categories) may be investigated.

In addition, the effect of concomitant use of MTX versus monotherapy on CZP plasma concentration and incidence of anti-CZP antibodies will be evaluated.

13.5 Planned efficacy and health outcomes analyses

Summary statistics will be presented for efficacy and health outcomes variables using the FAS.

All efficacy and health outcomes variables results will be presented overall and separately for the 2 CZP dose regimens (original CZP dose regimen, reduced CZP dose regimen).

The following efficacy variables are defined as secondary variables in this study:

- PedACR30, PedACR50, PedACR70, and PedACR90 response rates at Week 16 as compared to Baseline.

The following efficacy variables are defined as other variables:

- PedACR30, PedACR50, PedACR70, and PedACR90 response rates at every visit except Week 16 and Final Visit as compared to Baseline.

For PedACR30, PedACR50, PedACR70, and PedACR90, results will be presented overall and by Baseline weight strata, as well as by age (2 to 5 years, 6 to 11 years, and 12 to 17 years), by concomitant MTX use, and by anti-CZP antibody status.

- Change from Baseline in number of joints with active arthritis at every visit except Final Visit.
- Change from Baseline in number of joints with limitation of range of motion at every visit except Final Visit.
- Change from Baseline in Physician's Global Assessment of Disease Activity (VAS) at every visit except Final Visit.
- Change from Baseline in CHAQ at every visit except Final Visit.
- Change from Baseline in Parent's Assessment of Arthritis Pain (VAS) at every visit except Final Visit.
- Change from Baseline in Parent's Global Assessment of Overall Well-Being (VAS) at every visit except Final Visit.
- Ratio to Baseline in CRP at every visit except Final Visit.
- Change from Baseline in JADAS at every visit except Final Visit. The JADAS is a composite disease activity score including the Physician's Global Assessment of Disease Activity, the Parent's Global Assessment of Overall Well-Being, the active joint count, and CRP.
- Percentage of study participants with Clinically Inactive Disease (CID), as defined in Section 11.10, at every post-Baseline visit except Final Visit.

- Percentage of study participants with clinical remission on medication (CRM), as defined in Section 11.10, at every post-Baseline visit from Week 24 onwards except Final Visit.
- Time (in days) to CID.
- Time (in days) to CRM.
- Change from Baseline in DMS at every visit except Final Visit.
- Change from Baseline on FPS-R (child-reported, for study participants ages 5 to 11 years), daily during the first 7 days of treatment; Weeks 4, 12, 16, 24, and then every 8 weeks thereafter (for study participants enrolled prior to Protocol Amendment 9, visit frequency changes to every 16 weeks instead of every 8 weeks following implementation of Protocol Amendment 8) through the Early Discontinuation/End of Treatment Visit.
- Change from Baseline in JIA Pain VAS, daily during the first week of the study (acute and standard versions); Weeks 4, 12, 16, 24, and then every 8 weeks thereafter (for study participants enrolled prior to Protocol Amendment 9, visit frequency changes to every 16 weeks instead of every 8 weeks following implementation of Protocol Amendment 8) through the Early Discontinuation/End of Treatment Visit (standard version) for study participants ages 12 to 17 years.
- Change from Baseline in Fatigue Assessment Scale at every visit except Weeks 12 and 20, and Final Visit.
- Juvenile Arthritis School Attendance and Caregiver Work Productivity Survey responses at Baseline, Week 4, and every visit thereafter except Final Visit.

13.6 Handling of dropouts or missing data

For all binary efficacy endpoints assessing response, study participants who withdraw early will be considered as non-responders from that time point onwards. The exception is efficacy data for study participants who withdraw after Week 56: Per Protocol Amendment 7, these will not be imputed (as nonresponse or missing) and will be analyzed as observed.

For continuous efficacy endpoints, missing assessments will be imputed using the last observation carried forward (LOCF) approach. These summaries will be supported by observed case (OC) analyses. Per Protocol Amendment 7, missing assessments after Week 56 will no longer be imputed and will be analyzed as observed.

Data collected after the taking of rescue medication will be treated as missing for continuous efficacy endpoints and non-response for binary efficacy endpoints in all analyses except where specifically stated otherwise. See Section 7.8.2 for a list of medications which would result in data at only the next scheduled visit (and not all subsequent visits) being treated as missing/non-response. These data will then be imputed as for any other missing data. The exception is any rescue medication use that is initiated after Week 56: Per Protocol Amendment 7, efficacy data after any rescue medication use initiated after Week 56 will not be imputed (as nonresponse or missing) and will be analyzed as observed.

Missing or partial dates for safety evaluations will be imputed and full details of these algorithms will be presented in the SAP.

As discussed in Section 13.2, Baseline is defined as the last nonmissing pretreatment measurement, therefore if available, data from the Screening visit will be used as Baseline values, if these data are missing at Week 0.

No further imputations of any other missing data are planned (eg, efficacy data missing at random [MAR]).

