6.5 Withdrawal criteria

Study participants are free to withdraw from the study at any time, without prejudice to their continued care. Where possible, study participants discontinuing study medication should be encouraged to remain in the study.

A study participant may withdraw from the study at any time at his/her own request, or may be withdrawn at any time at the discretion of the investigator for safety, behavioral, compliance, or administrative reasons.

If the study participant withdraws consent for disclosure of future information, the sponsor may retain and continue to use any data collected before such a withdrawal of consent.

If a study participant withdraws from the study, he/she may request destruction of any samples taken and not tested, and the investigator must document this in the site study records.

See the Schedule of Activities for data to be collected at the time of study discontinuation and follow-up and for any further evaluations that need to be completed.

Study participants should be withdrawn from the study if any of the following events occur:

1. Study participant or legal representative withdraws his/her consent.
2. The sponsor or a regulatory agency requests withdrawal of the study participant.

Study participants must be permanently discontinued from study medication (but not necessarily from the study) if any of the following occurs:

1. Study participant/caregiver is noncompliant with the study procedures or medications in the opinion of the Investigator or Sponsor.
2. A study participant considered as having either a suspected new LTBI or who develops active TB or NTMB infection during the study (including but not limited to, conversion demonstrated by interferon-gamma release assay [IGRA] or other diagnostic means) must be immediately discontinued from IMP (refer to Section 10.7.9.8 for further details).
 - a) The study participant must be permanently withdrawn from the study if further examinations result in a diagnosis of active TB, NTMB infection, or if the study participant is diagnosed with LTBI. An Early Discontinuation visit must be scheduled as soon as possible, but not later than the next regular visit.

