7.8.3 Prohibited concomitant treatments (medications and therapies)

See [Table 6-1](#) for prohibitions prior to study entry. The following are prohibited at any time during the study:

- Nonbiologic DMARDs (other than MTX; see Section [7.8.1](#)) and biologic DMARDs.
- Any experimental (biological or non-biological) therapy (within or outside a clinical study).
- Live and live attenuated vaccinations including, but not limited to, oral polio, chicken pox (varicella), measles-mumps-rubella (MMR), nasal influenza, and rotavirus. No data are available on the response to live vaccinations or the secondary transmission of infection by live vaccines in study participants receiving CZP.

The concomitant use of these must result in the study participant's immediate discontinuation of CZP dosing and the study participant must be withdrawn from the study.

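### After Week 56 the binary response rates keep early withdrawals as failures but drop late withdrawals from the denominator, so they are neither non-responder-imputed nor observed-case rates

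*Protocol*

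**What the plan says.** Protocol Section 13.6 sets the rule for binary endpoints: "study participants who withdraw early will be considered as non-responders from that time point onwards". It then limits it: "The exception is efficacy data for study participants who withdraw after Week 56". Of those data it says that "these will not be imputed (as nonresponse or missing) and will be analyzed as observed". Rescue works in parallel. Under 13.6 and 7.8.2, rescue begun by Week 56 is failure from then on, and rescue begun later is ignored, with the data scored as collected.

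Continuous endpoints get a different rule in the same section. Missing values are carried forward, with observed-case analyses in support, and after Week 56 imputation stops for every missing assessment, whenever the participant left. The section closes with "No further imputations of any other missing data are planned".

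Two other places bear on who counts as withdrawn. Section 6.5 separates leaving the study from stopping certolizumab pegol (CZP): "Where possible, study participants discontinuing study medication should be encouraged to remain in the study". Its list of permanent stops is headed "Study participants must be permanently discontinued from study medication (but not necessarily from the study) if any of the following occurs", and item 4 of that list is use of prohibited medication. Section 7.8.3 says that the same use must result in "immediate discontinuation of CZP dosing and the study participant must be withdrawn from the study".

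**The concern.** The binary exception depends on when the participant withdrew, not on which visit is being analysed. A child who left at Week 40 is a failure at Week 104 and at every other late visit. A child who left at Week 60 is simply absent from the Week 104 rate. Rescue begun at Week 50 is permanent failure, while rescue begun at Week 60 never counts. The late rate therefore has one denominator built by two rules.

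Treatment is open-ended, and Section 13.5 reports PedACR30, 50, 70 and 90 at every visit except the Final Visit, overall and by dose regimen, weight, age, methotrexate use and antibody status. A table reader will take the late rates either as non-responder-imputed or as observed, and both are wrong. Groups that differ in when their members left can differ in reported response with no difference in clinical state. The plan adds observed-case support for continuous endpoints but none for binary ones, so no planned table would show the effect.

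**Working it through.** **Inputs**
- N = 186: Section 13.8 (156 + 30).
- Dropout of about 20%: Section 13.8. The plan's own figure reproduces: 100/(1 − 0.20) = 125.
- E, withdrawn by Week 56: 0.20 × 186 = 37.2, taken as 37. The 20% was stated in connection with 12 months of exposure, so using it for Week 56 is an approximation.
- r, response among those still observed: assumed 85%, with a range of 75% to 90%. The documents give no late response rate.
- L, withdrawn after Week 56: assumed 10%, 20% and 30% of 186, which is 19, 37 and 56.
- For simplicity: no rescue, no missed visits, and all 186 in the FAS.

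**Formulas**
- Rule in 13.6: r(N−E−L)/(N−L)
- Non-response throughout: r(N−E−L)/N
- Observed cases throughout: r

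**Results at r = 85%**

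| L | Still seen | Responders | Rule in 13.6 | Non-response throughout | Observed cases |
|---|---|---|---|---|---|
| 19 | 130 | 110.5 | 110.5/167 = 66.2% | 110.5/186 = 59.4% | 85.0% |
| 37 | 112 | 95.2 | 95.2/149 = 63.9% | 95.2/186 = 51.2% | 85.0% |
| 56 | 93 | 79.05 | 79.05/130 = 60.8% | 79.05/186 = 42.5% | 85.0% |

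With no late withdrawal the rule gives 0.85 × 149/186 = 68.1%. The reported rate thus falls from 68.1% to 60.8% as L rises from 0 to 30%, with response among those seen fixed at 85%. The cause is that the fixed 37 failures weigh more as the denominator shrinks.

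Over r = 75% to 90% and L = 10% to 30%, the rule lies 6.0 points (58.4 − 52.4) to 19.4 points (64.4 − 45.0) above uniform non-response. It lies 16.6 points (75.0 − 58.4) to 25.6 points (90.0 − 64.4) below observed cases.

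**Who counts as withdrawn**
Section 13.6 does not say what the participant withdraws from. Section 6.5 mostly uses withdrawal for the study and discontinuation for the drug, which favours leaving the study. Section 4.1.2, however, speaks of withdrawal of the drug. The two readings differ for a participant who stops CZP, stays in the study and takes no rescue: scored as observed under one, failure under the other.

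**Prohibited medication**
Under 7.8.3 the user leaves the study; under 6.5 item 4, not necessarily. The itemised rescue lists in 7.8.2 name neither biologics nor DMARDs other than methotrexate. The general definition that opens 7.8.2 could cover them, although it describes treatment given in addition to the study drug, which fits poorly once CZP has been stopped.

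**The case against.** The Week 56 switch is explicit, is attributed to Protocol Amendment 7, and is applied consistently in 13.6 and 7.8.2. The study has no control arm, the presentations are descriptive, and no test or decision rests on a late PedACR rate. All of this stands and limits the severity. It does not make the late rate interpretable, and being explicit about two rules does not turn them into one.

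Three stronger inferences are tempting, and the documents do not support them.

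- That the secondary endpoint is affected. It is fixed at Week 16, so the switch cannot reach it. Nor can the effect of CZP stoppers at Week 16 be sized: the protocol does not give the number off drug but still in the study. Stopping for clinical remission on medication (CRM) needs six months of inactive disease, so it cannot occur by then.
- That counting responders who are off CZP is an error. It can be a legitimate treatment-policy choice. What can be faulted is that the trigger is undefined, so the choice is not stated.
- That the conflict between 6.5 item 4 and 7.8.3 must give one participant opposite outcomes. Before Week 56, the general rescue definition in 7.8.2 plausibly makes a new JIA drug a failure either way. The conflict is real, but its effect on scoring is uncertain.

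**Conclusion.** The Week 56 point holds on the protocol's own text. Binary response rates at later visits are a hybrid that drifts with dropout timing and departs from the rule for continuous endpoints in the same section. In the illustration the hybrid is 6 to 19 points above uniform non-response and 17 to 26 points below observed cases. N and the 20% dropout come from Section 13.8; r, L and the absence of rescue are assumptions, so the formula is firm and the sizes are indicative.

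The reach is limited to efficacy variables classed as other. Error rates, sample size and the Week 16 endpoint are untouched. The undefined withdrawal term and the conflict between 6.5 and 7.8.3 are lesser, related points that need wording. The change should be made because it is specific and cheap.

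**What to change.** 1. In 13.6, for visits after Week 56, report binary endpoints as observed cases for everyone, showing n and the N still in the study, with full non-response imputation on the FAS alongside. Apply each rule to all participants whatever the date of withdrawal or rescue, and align 7.8.2.
2. State in 13.6 whether early withdrawal means leaving the study or stopping CZP. If it means stopping CZP, say how a stop for CRM is scored.
3. Reconcile 6.5 item 4 with 7.8.3 so that prohibited-medication use leads to one defined study status. For the analysis, name those drugs explicitly as treatment failure through Week 56 rather than rely on the general definition in 7.8.2.

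The cost is a few sentences and one extra table set, with no new data. Late rates will differ noticeably from the hybrid in both directions: observed cases higher, full non-response lower. The report should say so, and should note that observed cases describe only those who stayed.

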13.7 Interim analysis and data monitoring

A futility analysis of the PedACR30 response rate was performed after all active study participants enrolled on the reduced CZP dose had completed the Week 16 (Visit 8) assessments. If less than 50% of the study population enrolled on the reduced CZP dose regimen (Protocol Amendment 5) achieved a PedACR30 response at Week 16, the study was to be discontinued. The futility analysis confirmed that $\geq 50\%$ of the study population enrolled on the reduced CZP dose regimen achieved a PedACR30 response at Week 16. Given the descriptive nature of the data presentations, there were no statistical implications of this interim analysis. A further futility analysis will not be performed using the additional study participants that will be enrolled on the original CZP dose regimen following the implementation of Protocol Amendment 9.

In addition to the futility analysis, several interim analyses were planned, including interim analyses of PK data, and full interim analyses of PK, immunogenicity, safety, and efficacy endpoints, as described below.

Interim analyses of PK data

Per original protocol, if the pediatric plasma concentrations demonstrate that the geometric mean and median concentrations are below the adult 5th percentile or above the 95th percentile, the PK data will be used to re-evaluate the weight-based dose adjustment algorithm for pediatric study participants. Interim CZP plasma concentration data available at the time of Protocol Amendment 3 indicated that no change to the dosing algorithm was required. The protocol stated that if future interim analyses, which may include PopPK, indicate that plasma concentrations of JIA study participants are outside of the exposure range observed in previous adult RA studies, a revised pediatric dose algorithm will be derived. Any change in dose regimen will require a protocol amendment prior to implementation.

An interim analysis of PK data conducted following Protocol Amendment 3 compared CZP plasma concentration data from this study with CZP plasma concentrations observed previously in adult study participants with RA. Interim analysis of CZP plasma concentrations was started when 6 study participants in 1 of the age groups completed Week 12 (Visit 7). Comparisons were made between the Week 12 geometric mean and median values for the pediatric and adult study participants, as well as between the individual pediatric data and the adult 5th and 95th percentile and minimum and maximum observed values.

Based on results of this interim PopPK analysis (also described in Section 5.1), the dosing regimen was changed with Protocol Amendments 4 and 5, and the doses to be administered were reduced by 50% for all weight groups. This change was intended to achieve plasma

concentrations similar to the effective concentrations observed in previous studies in adult study participants with RA.

Interim analyses of PK, immunogenicity, safety, and efficacy endpoints

An interim analysis of PK, immunogenicity, safety, and efficacy endpoints was performed after all active study participants that were enrolled and treated prior to implementation of Protocol Amendment 9 had completed the Week 24 (Visit 10) assessments, and the results were reported separately. An interim analysis, including all enrolled participants, for all PK, immunogenicity, safety, and efficacy endpoints will be performed after all active study participants, including those enrolled following the implementation of Protocol Amendment 9, have completed the Week 24 (Visit 10) assessments.

Further interim analyses may be performed at the Sponsor's discretion as required.

A DSMB will periodically review emerging safety and efficacy data. The DSMB members will be independent of the Sponsor and Investigators. The DSMB members will be informed by the Patient Safety representative (or designee) of all SAEs at the time of expedited reporting and will periodically review emerging safety data (eg, SAEs, AEs, safety laboratory data) and efficacy data, as applicable, during the course of the study. Based on the safety data, the DSMB can recommend modifying/stopping the study.

13.8 Determination of sample size

Based upon the ICH guideline for the assessment of safety, it is planned to enroll a sufficient number of study participants to this study to have a minimum of 100 with at least 12 months continuous exposure to CZP. Assuming a dropout rate of approximately 20%, it was originally determined that 125 study participants would need to be enrolled. At the time of Protocol Amendment 5, 78 study participants had been enrolled according to the original CZP dose regimen, and it was planned to enroll a further 78 study participants on the reduced CZP dose regimen, so that a comparable number of study participants on the reduced CZP dose regimens could be analyzed. Thus, the total number of study participants planned to be enrolled was increased to 156 study participants. Assuming a Screening failure rate of 25%, it is planned to screen 195 study participants in total.

With Protocol Amendment 9, an additional 30 study participants will be enrolled on the original dose regimen with the aim to enroll at least 5 study participants in each weight range of 10 to <20kg (22 to <44lb), 20 to <40kg (44 to <88lb), and ≥ 40 kg (≥ 88 lb).

Prior to the start of study conduct, simulations using the adult population PK model in pediatric study participants with JIA suggested that the planned sample size of 125 study participants was adequate for PK assessment purposes. Individual apparent clearance (CL/F) and volume of distribution (V/F) were simulated for a total of 125 study participants (using the same approach presented in C87079 report addendum 08 Oct 2008 performed for 190 study participants). In all age groups, the standard errors of both PK parameters, CL/F and V/F, relative to their mean were substantially <20%, with values ranging from 5.5 to 7.0% for CL/F and from 4.6 to 7.5% for V/F. A tabular summary of the results is presented below.

Table 13-1 PK simulation results for 125-study participant study sample size

| Parameter | Age group (years) | Mean | Standard error | Standard error/ Mean (%) |
|-----------|-------------------|-------|----------------|-----------------------------|
| CL/F | 4 to 8 | 0.253 | 0.015 | 6.0 |
| | 9 to 12 | 0.356 | 0.025 | 7.0 |
| | 13 to 17 | 0.432 | 0.024 | 5.5 |
| V/F | 4 to 8 | 2.90 | 0.134 | 4.6 |
| | 9 to 12 | 4.80 | 0.358 | 7.5 |
| | 13 to 17 | 6.80 | 0.334 | 4.9 |

CL/F=apparent clearance; PK=pharmacokinetic; V/F=apparent volume of distribution

Data from all 186 study participants will be included in the final PopPK analysis, and therefore should allow CL/F and V/F to be determined with sufficient precision.

